## 9 DATA AND SAFETY MONITORING

### 9.1 Safety Monitoring

**Principal Investigator:** Accrual, efficacy and safety data will be monitored by the Principal Investigator, [name].

**NIH Intramural IRB.** Accrual and safety data will be monitored and reviewed annually by the Institutional Review Board (IRB). Prior to implementation of this study, the protocol and the proposed patient consent will be reviewed and approved by the properly constituted Institutional Review Board (IRB) operating according to Title 45 CFR 46. This committee will also approve all amendments to the protocol or informed consent, and conduct continuing annual review so long as the protocol is open to accrual or follow up of subjects or data and sample analysis is ongoing.

**NHLBI DSMB:** The NHLBI Data Safety and Monitoring Board will review the protocol at 6 to 12 month intervals, as determined by the DSMB. A progress report will be forwarded to the DSMB at these times and their recommendations will be expeditiously implemented. The DSMB may recommend early termination of the study for considerations of safety and efficacy.

**FDA:** An annual progress report, protocol amendments, and changes in the status of the protocol will be forwarded to the FDA using the following address:

Division of Drug Oncology Products, Office of Drug Products  
Center for Drug Evaluation and Research, FDA  
[name]  
[contact]

### 9.2 Event Characterization and Reporting

Events include adverse events (AE), serious adverse events (SAE), protocol deviations (PD), unanticipated problems (UP), and non-compliance.

The principal investigator will review all events (AEs, protocol deviations, UPs, SAEs) to determine the seriousness, expectedness, and reportability of the event. As required and/or needed, the principal investigator will review the events with the Sponsor to make the final determination of seriousness and reportability.

#### 9.2.1 Definitions

*Adverse Event (AE):* Any untoward or unfavorable medical occurrence in a human subject, including any abnormal sign (e.g., abnormal physical exam or laboratory finding), symptom, or disease, temporally associated with the subject's participation in the research, whether or not considered related to the research.

*Serious Adverse Event (SAE):* A serious adverse event that:

- results in death;
- is life-threatening (places the subject at immediate risk of death from the event as it occurred);
- results in in-patient hospitalization or prolongation of existing hospitalization;
- results in a persistent or significant incapacity;
- results in a congenital anomaly/birth defect; or
- based upon appropriate medical judgment, may jeopardize the subject's health and may require medical or surgical intervention to prevent one of the other outcomes listed in this definition.

*Suspected adverse reaction:* Suspected adverse reaction means any adverse event for which there is a reasonable possibility that the drug caused the adverse event. For the purposes of IND safety reporting, 'reasonable possibility' means there is evidence to suggest a causal relationship between the drug and the adverse event. A suspected adverse reaction implies a lesser degree of certainty about causality than adverse reaction, which means any adverse event caused by a drug.

*Serious event:* An event is serious if it meets the definition of a serious adverse event (above) or if it requires immediate corrective action by a PI and/or IRB to protect the safety, welfare or rights of subjects.

*Unexpected adverse reaction:* An adverse event or suspected adverse reaction is considered "unexpected" if it is not listed in the investigator brochure or is not listed at the specificity or severity that has been observed; or, if an investigator brochure is not required or available, is not consistent with the risk information described in the general investigational plan or elsewhere in the current application. "Unexpected", also refers to adverse events or suspected adverse reactions that are mentioned in the investigator brochure as occurring with a class of drugs or as anticipated from the pharmacological properties of the drug, but are not specifically mentioned as occurring with the particular drug under investigation.

*Unanticipated Problem (UP):* Any incident, experience, or outcome that meets all of the following criteria:

1. unexpected in terms of nature, severity, or frequency in relation to
  - a. the research risks that are described in the IRB-approved research protocol and informed consent document; Investigator's Brochure or other study documents; and
  - b. the characteristics of the subject population being studied; and
2. related or possibly related to participation in the research; and
3. places subjects or others at a greater risk of harm (including physical, psychological, economic, or social harm) than was previously known or recognized.

*Unanticipated Problem that is not an Adverse Event:* An unanticipated problem that does not fit the definition of an adverse event, but which may, in the opinion of the investigator, involves risk to the subject, affect others in the research study, or significantly impact the integrity of research data. For example, report occurrences of breaches of confidentiality, accidental destruction of study records, or unaccounted-for study drug.

*Protocol Deviation (PD)*: Any change, divergence, or departure from the IRB approved research protocol.

*Non-compliance*: The failure to comply with applicable NIH HRPP policies, IRB requirements, or regulatory requirements for the protection of human research. Noncompliance may be further characterized as:

1. **Serious non-compliance**: Non-compliance that:
  - a. Increases risks, or causes harm, to participants.
  - b. Decreases potential benefits to participants.
  - c. Compromises the integrity of the NIH HRPP.
  - d. Invalidates the study data.
2. **Continuing non-compliance**: Non-compliance that is recurring. An example may be a pattern of non-compliance that suggests a likelihood that, absent an intervention, non-compliance will continue. Continuing noncompliance could also include a failure to respond to IRB requests to resolve previous allegations of non-compliance.
3. **Minor (non-serious) non-compliance**: Non-compliance that, is neither serious nor continuing.

#### 9.2.2 Adverse Events Management:

All adverse events occurring during the study, including those observed by or reported to the research team, will be recorded. The AEs will be graded by severity utilizing CTCAE version 4.0. A copy of the criteria can be down-loaded at [http://evs.nci.nih.gov/ftp1/CTCAE/CTCAE\\_4.03\\_2010-06-14\\_QuickReference\\_8.5x11.pdf](http://evs.nci.nih.gov/ftp1/CTCAE/CTCAE_4.03_2010-06-14_QuickReference_8.5x11.pdf).

Eltrombopag has known and unknown toxicity profiles, thus, any observed or volunteered adverse events that are as listed in the Package Insert and/or Investigator's Brochure will not be reported unless (1) the adverse event was not present at baseline exam; (2) the adverse event is previously unknown (not on the label); (3) the adverse event is more severe than on the label; (4) the frequency of the adverse events increases above the listed frequency; or (5) meets the criteria for a serious adverse event.

**Non-hematologic abnormal laboratory findings** used to evaluate the safety of this protocol regimen will be collected to include any change from laboratory assessments done prior to first dose of eltrombopag that result in a progression to a grade 3 or 4 laboratory toxicity and/or are characterized by any of the following:

- Results in discontinuation from the study
- Is associated with clinical signs or symptoms
- Requires treatment or any other therapeutic intervention
- Is associated with death or another serious adverse event, including hospitalization
- Is judged by the Investigator to be of significant clinical impact
- If any abnormal laboratory result is considered clinically significant, the investigator will provide details about the action taken with respect to the test drug and about the patient's outcome.

In view of the underlying illness (bone marrow failure), many patients may enter the study with compromised hematologic indices that would be classified as toxicities. Therefore, we will look

at the relative decline of hematologic parameters and length of time to recovery to the patient's baseline as more significant than absolute values of these parameters. The laboratory toxicities will be graded by severity utilizing CTCAE version 4.0 or as mild, moderate, severe or life threatening according to the tables below:

**Attribution of Adverse Events:**

Criteria for Determining Category of Relationship of Clinical Adverse Events to Treatment		
1	Not related	This category applies to those adverse events which, after careful consideration, are clearly and incontrovertibly due to extraneous causes (disease, environment, etc.)
2	Unlikely (must have two)	In general, this category can be considered applicable to those adverse events which, after careful medical consideration at the time they are evaluated, are judged to be unrelated to the test drug. An adverse event may be considered unlikely if or when: 
 
1. It does not follow a reasonable temporal sequence from administration of the test drug.
 
2. It could readily have been produced by the subject's clinical state, environmental or toxic factors, or other modes of therapy administered to the subject.
 
3. It does not follow a known pattern of response to the test drug.
 
4. It does not reappear or worsen when the drug is re-administered.
 

3	Possibly (must have two)	This category applies to those adverse events for which, after careful medical consideration at the time they are evaluated, a connection with the test drug administration appears unlikely but cannot be ruled out with certainty. An adverse event may be considered possibly related if or when: 
 
1. It follows a reasonable temporal sequence from administration of the test drug.
 
2. It could not readily have been produced by the subject's clinical state, environmental or toxic factors, or other modes of therapy administered to the subject.
 
3. It follows a known pattern of response to the test drug.
 

4	Probably (must have three)	This category applies to those adverse events for which, after careful medical consideration at the time they are evaluated, are felt with a high degree of certainty to be related to the test drug. An adverse event may be considered probably related if or when: 
 
1. It follows a reasonable temporal sequence from administration of the test drug.
 
2. It could not be reasonably explained by the known characteristics of the subject's clinical state, environmental or toxic factors, or other modes of therapy administered to the subject.
 
3. It disappears or decreases on cessation or reduction in dose. There are important exceptions when an adverse event does not disappear upon discontinuation of the drug, yet drug-relatedness clearly exists (e.g., bone marrow depression, fixed drug eruptions, tardive dyskinesia).
 
4. It follows a known pattern of response to the test drug.
 

5	Definitely (must have all)	This category applies to those adverse events which, the Investigator feels are incontrovertibly related to test drug. An adverse event may be assigned an attribution of definitely related if or when: 
 
1. It follows a reasonable temporal sequence from administration of the test drug.
 
2. It could not be reasonably explained by the known characteristics of the subject's clinical state, environmental or toxic factors, or other modes of therapy administered to the subject.
 
3. It disappears or decreases on cessation or reduction in dose with re-exposure to drug. (Note: this is not to be construed as requiring re-exposure of the subject, however, a category of definitely related can only be used when a recurrence is observed.)
 
4. It follows a known pattern of response to the test drug.
 

**Grading of Adverse events:**

Grade	Severity	Description
1	Mild	asymptomatic or mild symptoms; clinical or diagnostic observations only; intervention not indicated.

2	Moderate	Moderate; minimal, local or noninvasive intervention indicated; limiting age-appropriate instrumental activities of daily living.
3	Severe or medically significant but not immediately life-threatening	Severe or medically significant but not immediately life-threatening; hospitalization or prolongation of hospitalization indicated; disabling; limiting self care activities of daily living (bathing, dressing and undressing, feeding self, using the toilet, taking medications, and not bedridden)
4	Life-threatening consequences	urgent intervention indicated.
5	Death	Death related to AE.

**Duration of adverse event collecting and reporting:** Thirty days after the last dose of study drug, adverse event reporting will be limited to those events considered possibly, probably, or definitely related to study drug.

### 9.2.3 Serious Adverse Events Management

Serious adverse events will be attributed as definitely (clearly related to the research), probably (likely related to the research), possibly (may be related to the research), unlikely (doubtfully related to the research) and unrelated (clearly not related to the research).

**Treatment related SAEs (TRSAEs)** are those attributed as definitely, probably, or possibly. As detailed in section 8.5 that will be monitored and considered for early stopping the study according to statistically determined criteria include death and any grade 4 toxicity considered to be probably or definitely related to study medication. [name], will serve as the independent monitor who reviews the attribution of TRSAEs.

Hospitalizations for administrative issues (to receive a transfusion) or upgrading to ICU for routine monitoring will not be reported as an SAE.

**Duration of Serious Adverse Event collecting and reporting:** The collection of SAEs will begin on the first day of initiation of the study drug and will continue along as the subject is on study. SAE reporting will continue as long as the subject remains on study.

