## 8.5 Study Stopping Rules

The study will be monitored to ensure that the occurrence of a specified set of treatment related serious adverse events (TRSAEs) that occur during the treatment period does not substantially exceed an anticipated rate. The following specified TRSAEs determined to be probably or definitely related to eltrombopag will be considered for early stopping of the study:

1. Death
2. Any Grade IV toxicity excluding readily reversible metabolic or laboratory abnormalities
3. Grade IV thrombosis/embolism
4. Progression to acute myeloid leukemia by WHO criteria (20% or greater bone marrow or peripheral blood blasts), or other marrow morphology changes deemed concerning by the investigators
5. Increase in reticulin fibrosis grade by 3 points above baseline

We anticipate the rate of these specified TRSAEs within the 16 to 20 weeks study period to be 20% or less. Following Geller et al. (Advances in Clinical Trial Biostatistics, 2004), our stopping rule is determined by a Bayesian approach. The stopping boundary for an experiment is reached if the Bayesian posterior probability that the true probability of developing one or more of the specified TRSAE's exceeds this benchmark rate of 20% is at least 90%. We take our prior distribution to be a beta distribution with parameters  $(\alpha, \beta) = (0.6, 2.4)$ . The parameter are chosen so that the mean  $\alpha / (\alpha + \beta) = 0.2$  as the expected proportion of specified TRSAE's and the sum  $\alpha + \beta = 3$  as the "worth" we place on our prior clinical opinion. This indicates that the relative weight we place on our prior opinion is  $3/30=10\%$  of the weight we will place on the results of the new study. Hence when we make decisions about stopping the study, the data from this study will dominate over the prior opinion. Since we have seen in the past that the first few subjects to be accrued are possibly sicker than the rest of the subjects in the sample, we will start safety monitoring when 3 or more subjects have developed a TRSAE. The following table summarizes the threshold numbers for stopping the study.

Number of subjects in the experiment	Stop if the number of subjects who have developed any of the specified TRSAE's reaches:
$\leq 6$	3
$\leq 9$	4
$\leq 13$	5
$\leq 17$	6

Number of subjects in the experiment	Stop if the number of subjects who have developed any of the specified TRSAE's reaches:
≤ 21	7
≤ 25	8

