#### **9.2.4.3 NHLBI DSMB Reporting:**

Reports of serious adverse events that are unexpected and thought to be related to the experimental drug will also be forwarded as soon as possible but no later than seven (7) days in the case of death or life-threatening serious adverse events or within fifteen (15) days after the occurrence of all other forms of serious adverse event to the Data and Safety Monitoring Board (DSMB). A summary of events will be included in DSMB reports for review by the DSMB.

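### The independent monitor checks attribution only for events already called at least possibly related, so a section 8.5 event wrongly called unlikely or unrelated cannot be corrected into the safety count

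*Combined protocol and SAP*

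**What the plan says.** **What counts.** Section 8.5 sets the filter: "The following specified TRSAEs determined to be probably or definitely related to eltrombopag will be considered for early stopping of the study". The list has five items: death, "Any Grade IV toxicity excluding readily reversible metabolic or laboratory abnormalities", Grade IV thrombosis/embolism, "Progression to acute myeloid leukemia by WHO criteria" (or other concerning marrow changes), and an increase in reticulin fibrosis. The boundary is 3 affected subjects by the 6th, 4 by the 9th, 5 by the 13th, 6 by the 17th, 7 by the 21st and 8 by the 25th.

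**What the monitor sees.** Section 9.2.3 says that TRSAEs "are those attributed as definitely, probably, or possibly". It then names a person who "will serve as the independent monitor who reviews the attribution of TRSAEs".

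**Who attributes.** The attribution table in section 9.2.2 is written for the investigator. Its top category covers events that "the Investigator feels are incontrovertibly related to test drug". *Unlikely* needs two of four criteria, one of which is: "It could readily have been produced by the subject's clinical state, environmental or toxic factors". *Probably* needs three of four. *Definitely* needs all four, including an observed recurrence.

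**Other routes.** Section 9.2.4.1 sends SAEs to the Clinical Director within 14 days and deaths within 7 days (unanticipated problems go by their own route). Section 9.2.4.4 sends SAEs to the sponsor within 24 to 72 hours. Section 9.2.4.3 restricts expedited DSMB reports: "Reports of serious adverse events that are unexpected and thought to be related to the experimental drug will also be forwarded". It also gives the DSMB a periodic summary of events with no relatedness filter. Under section 9.1 the DSMB meets every 6 to 12 months and may recommend early termination.

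**AML.** Section 2.7 states that progression to AML sets off a stopping rule and attaches no attribution condition.

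**The concern.** The trial is non-randomized and has no control rate, so attribution alone decides which events reach the safety boundary. Two errors are possible: an unrelated event called related, and a related event called unrelated. An independent check should be able to correct both. As worded, this one corrects the first, and can raise an event called *possibly*, but it cannot reach an event called *unlikely* or *unrelated*.

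That second error is the one that hides harm, and it is plausible here. Sections 2.1 and 2.2 describe fatal bleeding and infection as part of MDS, and Appendix B describes evolution to AML. Such an event will often meet the clinical-state criterion for *unlikely*. Section 2.7 nevertheless treats AML progression as a theoretical drug risk. Where disease course and drug effect look alike, a second reader of negative calls matters most.

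**Working it through.** **Step 1. Trace an 8.5-type event through sections 9.2.3 and 8.5.**

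| First attribution | TRSAE under 9.2.3? | Monitor reviews it? | Counts under 8.5? |
|---|---|---|---|
| Definitely or probably | Yes | Yes; may lower it | Yes |
| Possibly | Yes | Yes; may raise it | Only if raised |
| Unlikely or unrelated | No | No | No |

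The last row has no exit. Section 9.2 gives the investigator and sponsor seriousness, expectedness and reportability, not relatedness for the 8.5 count. Small parts of the reporting section were absent from the text available for this review, so this statement covers the visible text.

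**Step 2. Reproduce the plan's operating characteristics.** Inputs are the printed boundary b(n) and 25 independent subjects, each with event probability p (section 8.5). Let f(n,k) be the probability of k counted events after n subjects without having stopped. Then

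f(n,k) = f(n−1,k)(1−p) + f(n−1,k−1)p for k < b(n),

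and any mass reaching k ≥ b(n) is added to the stopping probability.

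| p | 0.10 | 0.20 | 0.25 | 0.30 | 0.40 |
|---|---|---|---|---|---|
| Plan, stopped | 2.4% | 22.7% | 41.5% | 61.5% | 89.7% |
| Exact, stopped | 2.4% | 22.5% | 41.4% | 61.5% | 89.7% |
| Exact, mean subjects | 24.6 | 21.8 | 19.3 | 16.4 | 11.0 |

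The mean subjects equal the plan's. At p = 0.20 the standard error of 100,000 simulations is √(0.225 × 0.775 / 100,000) = 0.13 percentage points, so the 0.2-point gap is simulation noise.

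**Step 3. Let some related events be miscalled.** Let m be the share of subjects with a related event whose event is called *unlikely* or *unrelated* and stays so. The boundary then sees p × (1 − m). The documents give no value for m; the values below are assumptions.

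| m | True 30%: counted rate | Stopped | True 40%: counted rate | Stopped |
|---|---|---|---|---|
| 0 | 0.30 | 61.5% | 0.40 | 89.7% |
| 10% | 0.30 × 0.9 = 0.27 | 49.6% | 0.40 × 0.9 = 0.36 | 81.1% |
| 20% | 0.30 × 0.8 = 0.24 | 37.4% | 0.40 × 0.8 = 0.32 | 68.8% |
| 50% | 0.30 × 0.5 = 0.15 | 9.1% | 0.40 × 0.5 = 0.20 | 22.5% |

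At a true 30% with one third miscalled, the counted rate is 0.30 × 2/3 = 0.20. Stopping is then 22.5% and mean subjects rise from 16.4 to 21.8.

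**Step 4. What a wider review could recover.** If the monitor restores a fraction r of the miscalled events, the counted rate is p × (1 − m(1 − r)). With p = 0.30, m = 20% and r = one half (an assumption), this is 0.30 × (1 − 0.20 × 0.5) = 0.27, so stopping returns from 37.4% to 49.6%, not to 61.5%.

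**The case against.** **Other oversight exists.** A reader might infer that these events escape independent review altogether. They do not. The DSMB gets an unfiltered summary and can recommend termination, and the Clinical Director and sponsor receive deaths and SAEs whatever the attribution. The sponsor's IND reporting decision also involves causality, including an aggregate comparison for known consequences of the disease. All of this stands. What remains is that none of these routes is described as changing an attribution or feeding the 8.5 count.

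**AML.** A reader might infer that AML called unrelated can never set off a stopping rule. Section 2.7 says otherwise without condition. For AML the documents conflict, and they do not establish the stronger reading.

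**Loose drafting.** Reviewing the attribution of TRSAEs could mean deciding which SAEs qualify as TRSAEs. That intention is possible, but the definition just before the sentence points the other way.

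**The numbers.** The shares are assumed, and full recovery by the monitor is unrealistic: the same criteria would apply, and a death cannot show the recurrence that *definitely* requires. The 20% benchmark is also set for events after attribution. These points stand. They limit the figures to illustration and leave the gap in scope untouched.

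**Conclusion.** The concern holds in a limited form. As written, independent attribution review cannot correct a false *unlikely* or *unrelated* call, and such an event cannot enter the 8.5 count. For AML, sections 2.7 and 8.5 contradict each other and must be reconciled.

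A reader might go further and conclude that the count is biased downward by a known amount. The documents do not support that: they give no misattribution rate, and over-attribution is also possible. What they show is a check that cannot correct one kind of error. The fall from 61.5% to between 49.6% and 22.5% at a true 30% assumes that 10% to one third of related events are miscalled, independently across subjects, with none recovered. It shows that the printed operating characteristics depend on correct attribution; it does not estimate the loss in this trial. This is a cheap improvement to the plan and does not invalidate the stopping rule.

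**What to change.** In section 9.2.3, replace the monitor sentence with text to this effect: *The independent monitor reviews the attribution of every event that meets an event definition in section 8.5, with that section's grade limits and exclusions, whatever its first attribution. An event first called probably or definitely related counts towards the boundary at once, pending this review.* Add one sentence saying whose attribution governs the count when investigator and monitor differ; this also settles how an event first called *possibly* comes to be counted.

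Keep the count of related events and the 20% benchmark. Moving to all-cause events would need a newly justified benchmark. Reconcile sections 2.7, 8.5 and 9.2.3, including whether AML progression is subject to a relatedness condition.

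The cost is a few sentences of text. The monitor is already appointed and would read a few more SAE reports in a trial capped at 30 subjects. Because events called related count immediately, the review does not delay the boundary for them.
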